### 12.1.2 Pembrolizumab (Patients Enrolled in Parts 1b, 1c, and 3)

Pembrolizumab is a potent humanized immunoglobulin G4 (IgG4) monoclonal antibody (mAb) with high specificity of binding to the programmed cell death 1 (PD-1) receptor, thus inhibiting its interaction with programmed cell death ligand 1 (PD-L1) and programmed cell death ligand 2 (PD-L2). Based on preclinical in vitro data, pembrolizumab has high affinity and potent receptor blocking activity for PD-1. Pembrolizumab has an acceptable preclinical safety profile and is in clinical development as an intravenous (IV) immunotherapy for advanced malignancies.

Keytruda™ (pembrolizumab) is indicated for the treatment of patients across a number of indications. For more details on specific indications refer to the Investigator brochure.

The safety profile of pembrolizumab is fully described in the pembrolizumab Label/Investigator's Brochure and primarily consists of immune-related adverse events (ir-AEs) due to activation and proliferation of T-cells. Ir-AEs can affect any organ or tissue, but most frequently occur in the skin (rash), gastrointestinal system (diarrhea/colitis), liver (hepatitis), lungs (pneumonitis), endocrine system (endocrinopathies due to inflammation of the pituitary, thyroid and adrenals), and kidneys (nephritis). The management of these toxicities is described in the pembrolizumab Label/Investigator's Brochure but generally includes holding drug for moderate (Grade 2) toxicities and using systemic immunosuppression for severe (Grade 3/4) or prolonged moderate (> 1 week) toxicities. Additional immunosuppression (e.g., anti-TNF $\alpha$  therapy, infliximab) may be used if IV steroids are ineffective.

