Study drug-related creatinine increase  (patients with CrCl > 50 mL/min at baseline)	Grade 2 (> 1.5-3.0 X baseline OR > 1.5-3.0 X ULN)	Weekly testing of serum creatinine during interruption of study drug.	
 
Interrupt study drug.
 
1st event: Restart at same dose upon resolution to ≤ Grade 1.
 
2nd event: Restart at 25 mg BID upon resolution to ≤ Grade 1.
 

	Grade 3 (> 3.0 baseline; > 3.0-6.0 X ULN) or 4 (> 6.0 X ULN)	Weekly testing of serum creatinine during interruption of study drug.	
 
Interrupt study drug and do weekly serum creatinine testing and urinalysis until serum creatinine returns to ≤ Grade 1. Restart study drug at 25 mg BID.
 
If after 4 weeks the serum creatinine has not recovered to ≤ Grade 1, permanently discontinue study drug.
 
If after restarting study drug the toxicity reoccurs, permanently discontinue study drug.
 

Suspected immune-related adverse event (irAE) including: 
 
Colitis
 
Pneumonitis
 
Dermatitis
 
Hepatitis
 
Hypophysitis
 
Adrenal insufficiency
 
Type I diabetes mellitus
 
Nephritis
 
	Grade 1	
 
Symptomatic therapy, as appropriate
 
	No change
	Grade 2	
 
If > 5 days, 0.5 to 1 mg/kg/day prednisone. If worsening or no improvement, increase to 1 to 2 mg/kg/day prednisone equiv. and consider IV.
 
	
 
Interrupt study drug.
 
1st event: Restart at same dose upon resolution to ≤ Grade 1.
 
2nd event: Restart one dose level lower for second event of the same AE.
 

	Grade 3	
 
1 to 2 mg/kg/day prednisone equiv. Consider IV.
 
	
 
Interrupt study drug.
 
1st event: Consider restarting at next lower dose level upon resolution to ≤ Grade 1.
 
2nd event: Permanently discontinue.
 

	Grade 4	
 
1 to 2 mg/kg/day prednisone equiv. Consider IV.
 
	
 
Permanently discontinue.
 

**Table 12.1-1: INCB001158 Dose Modification Guidelines for Adverse Events in Patients Receiving INCB001158 (All Parts) (Continued)**

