Pneumonitis	Grade 2	Withhold	
 
Administer corticosteroids (initial dose of 1 - 2 mg/kg prednisone or equivalent) followed by taper
 
Add prophylactic antibiotics for opportunistic infections
 
	
 
Monitor participants for signs and symptoms of pneumonitis
 
Evaluate participants with suspected pneumonitis with radiographic imaging and initiate corticosteroid treatment
 

	Recurrent Grade 2, Grade 3 or 4	Permanently discontinue		
Diarrhea / Colitis	Grade 2 or 3	Withhold	
 
Administer corticosteroids (initial dose of 1 - 2 mg/kg prednisone or equivalent) followed by taper
 
	
 
Monitor participants for signs and symptoms of enterocolitis (ie, diarrhea, abdominal pain, blood or mucus in stool with or without fever) and of bowel perforation (ie, peritoneal signs and ileus)
 
Participants with <math>\geq</math>Grade 2 diarrhea suspecting colitis should consider GI consultation and performing endoscopy to rule out colitis
 
Participants with diarrhea/colitis should be advised to drink liberal quantities of clear fluids. If sufficient oral fluid intake is not feasible, fluid and electrolytes should be substituted via IV infusion
 

	Recurrent Grade 3 or Grade 4	Permanently discontinue		

**Table 12.1-2: Dose Modification and Toxicity Management Guidelines for Immune-Related Adverse Events Associated With Pembrolizumab (Parts 1b, 1c, and 3) (Continued)**

irAEs	Toxicity Grade (CTCAE V4.0)	Action With Pembrolizumab	Corticosteroid and/or Other Therapies	Monitoring and Follow-up
AST or ALT elevation or Increased Bilirubin	Grade 2 a	Withhold	
 
Administer corticosteroids (initial dose of 0.5 - 1 mg/kg prednisone or equivalent) followed by taper
 
	
 
Monitor with liver function tests (consider weekly or more frequently until liver enzyme value returned to baseline or is stable)
 

	Grade 3 b or 4 c	Permanently discontinue	
 
Administer corticosteroids (initial dose of 1 - 2 mg/kg prednisone or equivalent) followed by taper
 
	

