Type 1 diabetes mellitus (T1DM) or Hyperglycemia	New onset T1DM or Grade 3 or 4 hyperglycemia associated with evidence of $\beta$ -cell failure	Withhold d	
 
Initiate insulin replacement therapy for participants with T1DM
 
Administer anti-hyperglycemic in participants with hyperglycemia
 
	
 
Monitor participants for hyperglycemia or other signs and symptoms of diabetes
 

Hypophysitis	Grade 2	Withhold	
 
Administer corticosteroids and initiate hormonal replacements as clinically indicated
 
	
 
Monitor for signs and symptoms of hypophysitis (including hypopituitarism and adrenal insufficiency)
 

	Grade 3 or 4	Withhold or permanently discontinue d		
Hyperthyroidism	Grade 2	Continue	
 
Treat with non-selective beta-blockers (eg, propranolol) or thionamides as appropriate
 
	
 
Monitor for signs and symptoms of thyroid disorders
 

	Grade 3 or 4	Withhold or permanently discontinue d		
Hypothyroidism	Grade 2, 3, 4	Continue	
 
Initiate thyroid replacement hormones (eg, levothyroxine or liothyronine) per standard of care
 
	
 
Monitor for signs and symptoms of thyroid disorders
 

**Table 12.1-2: Dose Modification and Toxicity Management Guidelines for Immune-Related Adverse Events Associated With Pembrolizumab (Parts 1b, 1c, and 3) (Continued)**

irAEs	Toxicity Grade (CTCAE V4.0)	Action With Pembrolizumab	Corticosteroid and/or Other Therapies	Monitoring and Follow-up
Nephritis: grading according to increased creatinine or acute kidney injury	Grade 2	Withhold	
 
Administer corticosteroids (prednisone 1 – 2 mg/kg or equivalent) followed by taper
 
	
 
Monitor changes of renal function
 

	Grade 3 or 4	Permanently discontinue		
Myocarditis	Grade 1 or 2	Withhold	
 
Based on severity of AE administer corticosteroids
 
	
 
Ensure adequate evaluation to confirm etiology and/or exclude other causes
 

	Grade 3 or 4	Permanently discontinue		

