In addition, patients with severe enterocolitis that are receiving INCB001158 monotherapy will have INCB001158 permanently discontinued, whereas, for patients receiving INCB001158/pembrolizumab combination, pembrolizumab will be permanently discontinued and INCB001158 will be withheld. Restarting INCB001158 may be considered in INCB001158/pembrolizumab combination patients if enterocolitis is not a toxicity associated with monotherapy INCB001158.

In patients with moderate enterocolitis, pembrolizumab should be withheld and antidiarrheal treatment should be started. If symptoms are persistent for more than one week, systemic corticosteroids should be initiated (e.g., 0.5 mg/kg/day of prednisone or equivalent). When symptoms improve to Grade 1 or less, corticosteroid taper should be started and continued over at least 1 month. Regarding guidelines for continuing treatment with INCB001158 and pembrolizumab, see [Table 12.1-2](#).

All patients who experience diarrhea should be advised to drink liberal quantities of clear fluids. If sufficient oral fluid intake is not feasible, fluid and electrolytes should be substituted via IV infusion.

**Nausea/vomiting:** Nausea and vomiting should be treated aggressively, and consideration should be given in subsequent cycles to the administration of prophylactic antiemetic therapy according to standard institutional practice. Patients should be strongly encouraged to maintain liberal oral fluid intake. Since nausea/vomiting can be a symptom of hyperammonemia, there should be a low threshold to test plasma ammonia levels for patients with nausea, vomiting, or new onset anorexia.

**Anemia:** Transfusions and/or erythropoietin may be utilized as clinically indicated for the treatment of anemia, but should be clearly noted as concurrent medications.

**Neutropenia:** Prophylactic use of colony-stimulating factors including Granulocyte Colony-Stimulating Factor (G-CSF), pegylated G-CSF or Granulocyte Macrophage Colony-Stimulating Factor (GM-CSF) is not allowed in this study. Therapeutic use of G-CSF is allowed in patients with Grade 3-4 febrile neutropenia.

**Thrombocytopenia:** Transfusion of platelets may be used if clinically indicated. Idiopathic thrombocytopenic purpura (ITP) should be ruled out before initiation of platelet transfusion.

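### Grade 2 colitis on the combination: Section 12.1.3.3 delays and lowers corticosteroids relative to Table 12.1-2, and no text says which rule applies

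*Protocol*

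**What the plan says.** All references are to the protocol.

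- **Section 12.1.3.3, Diarrhea.** "In patients with moderate enterocolitis, pembrolizumab should be withheld and antidiarrheal treatment should be started". Then: "If symptoms are persistent for more than one week, systemic corticosteroids should be initiated (e.g., 0.5 mg/kg/day of prednisone or equivalent". The paragraph does point to Table 12.1-2, but for a different purpose: "Regarding guidelines for continuing treatment with INCB001158 and pembrolizumab, see" that table.
- **Table 12.1-2 (Parts 1b, 1c and 3).** For Grade 2 or 3 diarrhea/colitis: "Administer corticosteroids (initial dose of 1 - 2 mg/kg prednisone or equivalent) followed by taper". The pneumonitis row uses the same words and adds: "Evaluate participants with suspected pneumonitis with radiographic imaging and initiate corticosteroid treatment". For Grade 2 nephritis: "Administer corticosteroids (prednisone 1 – 2 mg/kg or equivalent) followed by taper".
- **Table 12.1-1 (all parts).** For a suspected Grade 2 irAE, with colitis, pneumonitis and nephritis all named, a steroid starts only beyond "5 days, 0.5 to 1 mg/kg/day prednisone. If worsening or no improvement, increase to 1 to 2 mg/kg/day prednisone equiv. and consider IV".
- **Sections 12.1.2 and 12.1.1.** Section 12.1.2 says that management of pembrolizumab toxicity "generally includes holding drug for moderate (Grade 2) toxicities", and it keeps systemic immunosuppression for severe events or moderate events lasting more than 1 week. Section 12.1.1, on irAEs that INCB001158 might cause, gives corticosteroids for Grade 3 or higher events or for events lasting more than two weeks with little or no improvement.
- **Section 12.1.3.1.** AE management and dose modification for INCB001158 are placed in Table 12.1-1. Dose modification and toxicity management for pembrolizumab-associated irAEs are placed in Table 12.1-2. For irAEs on the combination, dose interruption and modification follow the two tables, each for its own drug.

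**The concern.** A site treating a combination patient with Grade 2 colitis finds three instructions on when to start a corticosteroid and at what dose. The most cautious in timing and dose is Table 12.1-2, which Attachment 12 says was updated in this amendment to the manufacturer's most recent guidelines. Attachment 12 lists no matching change to the enterocolitis paragraph of Section 12.1.3.3, which is the slowest and lowest of the three. At stake is patient safety: delayed, lower-dose steroid treatment of an immune-related event, chosen by which page the site happens to read.

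**Working it through.** The plan gives no statistical figure to reproduce here. The check sets the instructions side by side and sizes the difference.

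| Source | Applies to | Steroid start, Grade 2 colitis | Starting dose |
|---|---|---|---|
| Table 12.1-2, Diarrhea/Colitis row | Parts 1b, 1c, 3 | no stated wait | 1 to 2 mg/kg |
| Table 12.1-1, suspected irAE row | all parts | after more than 5 days | 0.5 to 1 mg/kg/day, rising to 1 to 2 if worse or no better |
| Section 12.1.3.3, moderate enterocolitis | patients on pembrolizumab | after more than 7 days | 0.5 mg/kg/day, as an example |

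**Same event, same patients.** Sections 12.1.1 and 12.1.2 and the severity scale in Section 16.1.2 all equate moderate with Grade 2. The Section 12.1.3.3 paragraph is aimed at combination patients, because it tells sites to withhold pembrolizumab. Table 12.1-1 includes these patients by its all-parts title.

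**No stated wait.** For colitis this is read from silence, but the silence has some weight. The row of Table 12.1-2 for all other irAEs limits its Grade 2 instruction to persistent events; the colitis row has no such limit.

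**Dose ratios, reading the Table 12.1-2 dose as daily.**
- Table 12.1-2 over the Section 12.1.3.3 example: 1/0.5 = 2 and 2/0.5 = 4.
- Table 12.1-2 over the Table 12.1-1 starting dose: 1/0.5 = 2 (lower ends) and 2/1 = 2 (upper ends). The two ranges meet at 1 mg/kg.

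**In milligrams, at assumed body weights.**

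| Weight | Table 12.1-2 | Table 12.1-1 | Section 12.1.3.3 |
|---|---|---|---|
| 50 kg | 50 to 100 mg | 25 to 50 mg/day | 25 mg/day |
| 70 kg | 70 to 140 mg | 35 to 70 mg/day | 35 mg/day |
| 90 kg | 90 to 180 mg | 45 to 90 mg/day | 45 mg/day |

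**Does any text settle it?** Between the two tables, partly. Section 12.1.3.1 places toxicity management of pembrolizumab-associated irAEs in Table 12.1-2, and Section 12.1.3 defines irAEs as events occurring while receiving pembrolizumab. Section 12.1.3.3 is separate text, and its only link to Table 12.1-2 concerns continuing study treatment. No sentence ranks its steroid rule against the table.

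**Where the sources agree.** The Grade 3 colitis steroid dose is 1 to 2 mg/kg in both tables and in Section 12.1.3.3. For Grade 2 liver events both tables give 0.5 to 1 mg/kg, so there is no dose conflict.

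**The case against.** The strongest reply has four parts.

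1. **Safeguards.** Section 12.1.3.1 calls the parameters guidelines only, tells investigators to err on the side of caution, and asks for contact with the Medical Monitor when systemic immunosuppression is required. Section 12.1.3.3 asks for immediate discussion of any irAE of Grade 2 or higher and names colitis. Table 12.1-2 and Section 12.1.3.3 agree on withholding pembrolizumab. All of this stands and limits the harm. It does not settle which rule applies: Section 12.1.3.1 also asks sites to call if they prefer to deviate from the guidelines, and with three rules a site cannot tell what counts as deviating.

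2. **The one-week trigger is not an isolated slip.** Section 12.1.2 gives the same trigger when it summarises label and Investigator's Brochure management. This stands, and it means that editing Section 12.1.3.3 alone would leave a second one-week statement in conflict with the table.

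3. **The size is soft.** The 0.5 mg/kg/day is an example, Table 12.1-2 does not say per day, and Table 12.1-1 escalates to 1 to 2 mg/kg/day. This stands for the dose ratios. It does not touch the difference in timing.

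4. **The clinically right rule depends on the pembrolizumab label.** Section 12.1.3.3 says to use its guidance together with the label, which is not in the documents. This stands, so the choice needs clinical confirmation. The label reference itself ranks nothing.

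A reader might also infer an equal, unresolved conflict for Grade 2 pneumonitis and nephritis, where Table 12.1-2 gives 1 to 2 mg/kg and Table 12.1-1 gives 0.5 to 1 mg/kg/day after more than 5 days. The documents do not support that strength. For those events only the two tables compete, and Section 12.1.3.1 assigns pembrolizumab irAE toxicity management to Table 12.1-2. Its sentence naming both tables for combination irAEs covers dose interruption and modification, split by drug; it does not send the steroid choice to both.

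**Conclusion.** The point holds for Grade 2 (moderate) colitis in combination patients and should be fixed. Section 12.1.3.3 starts a steroid after more than a week, at for example 0.5 mg/kg/day. Table 12.1-2 gives an initial 1 to 2 mg/kg with no stated wait, and Table 12.1-1 lies between them. The Section 12.1.3.3 example is 2- to 4-fold below the Table 12.1-2 range, assuming that the table's dose is daily. Sections 12.1.2 and 12.1.1 add general triggers of more than one and more than two weeks. Pneumonitis and nephritis need only a minor clarification.

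Confidence in the textual contradiction is high; which rule is clinically right is for the sponsor's experts. The number of patients exposed may be small: Attachment 12 speaks of a limited number still on treatment, and Section 17.0 permits a database lock with no more than 10 subjects on treatment. The documents do not say how many combination patients remain. A reader might infer consequences for DLT counts, dose escalation or SAP outputs. None has been shown, and none is claimed.

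**What to change.** 1. In Section 12.1.3.3, for combination patients, replace the steroid sentence for moderate enterocolitis with a reference to the Diarrhea/Colitis row of Table 12.1-2. Align the more-than-1-week wording in Section 12.1.2 with that table.
2. In Section 12.1.3.1, add one sentence: where Tables 12.1-1 and 12.1-2 differ on corticosteroid start or dose for an irAE in a patient receiving pembrolizumab, Table 12.1-2 governs. Leave Table 12.1-1 applicable to all parts for INCB001158 dose modification, and for irAEs with no specific steroid instruction in Table 12.1-2. Confining its steroid text to monotherapy would go too far: the table is titled for all parts, and Attachment 9 records that INCB001158 AE management was deliberately clarified to apply beyond monotherapy.
3. Have the sponsor's clinical experts confirm both changes against the current pembrolizumab label.

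The cost is protocol wording in three sections, through the next amendment or a letter to sites, with no new procedures.

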**Table 12.1-3: Pembrolizumab Infusion Reaction Dose Modification and Treatment Guidelines**

NCI CTCAE Grade	Treatment	Premedication at Subsequent Dosing
Grade 1 Mild reaction; infusion interruption not indicated; intervention not indicated	Increase monitoring of vital signs as medically indicated until the patient is deemed medically stable in the opinion of the investigator.	None
Grade 2 Requires therapy or infusion interruption but responds promptly to symptomatic treatment (e.g., antihistamines, NSAIDs, narcotics, IV fluids); prophylactic medications indicated for ≤ 24 hours.	Stop Infusion. Additional appropriate medical therapy may include but is not limited to: 
 
• IV fluids
 
• Antihistamines
 
• NSAIDs
 
• Acetaminophen
 
• Narcotics
 
 Increase monitoring of vital signs as medically indicated until the patient is deemed medically stable in the opinion of the investigator. If symptoms resolve within 1 hour of stopping drug infusion, the infusion may be restarted at 50% of the original infusion rate (e.g., from 100 mL/hr. to 50 mL/hr). Otherwise dosing will be held until symptoms resolve and the patient should be premedicated for the next scheduled dose. Patients who develop Grade 2 toxicity despite adequate premedication should be permanently discontinued from further study drug treatment.	Patient may be premedicated 1.5 hr (± 30 minutes) prior to infusion of _____ with: Diphenhydramine 50 mg PO (or equivalent dose of antihistamine). Acetaminophen 500-1000 mg PO (or equivalent dose of analgesic).
Grades 3 or 4 Grade 3: Prolonged (i.e., not rapidly responsive to symptomatic medication and/or brief interruption of infusion); recurrence of symptoms following initial improvement; hospitalization indicated for other clinical sequelae (e.g., renal impairment, pulmonary infiltrates) Grade 4: Life-threatening; pressor or ventilator support indicated	Stop Infusion. Additional appropriate medical therapy may include but is not limited to: 
 
• Epinephrine**
 
• IV fluids
 
• Antihistamines
 
• NSAIDs
 
• Acetaminophen
 
• Narcotics
 
• Oxygen
 
• Pressors
 
• Corticosteroids
 
 Increase monitoring of vital signs as medically indicated until the patient is deemed medically stable in the opinion of the investigator. Hospitalization may be indicated. **In cases of anaphylaxis, epinephrine should be used immediately. Patient is permanently discontinued from further study drug treatment.	No subsequent dosing.
Appropriate resuscitation equipment should be available at the bedside and a physician readily available during the period of drug administration. For further information, please refer to the Common Terminology Criteria for Adverse Events v4.0 (CTCAE) at http://ctep.cancer.gov .		

## 12.2 Dose Adjustments, Infusion Delays, and Missed Doses

Missed doses of INCB001158 should be skipped. If a patient forgets to take a dose of INCB001158 study drug and he/she is outside of the allotted window period ( $\pm 6$  hr), he/she should be instructed to skip that dose and NOT to take extra INCB001158 study drug at their next administration.

In the case that an infusion cannot be administered at a scheduled visit, it has to be administered as soon as possible. If the delay is between 1 and 7 days, the procedures at the original scheduled visit should be performed, and subsequent visits will follow every 2 weeks (the infusion at the original schedule visit will be considered a missed dose). Patients with infusion delays  $> 35$  days should discontinue from the study unless approved by the Medical Monitor in settings where benefit/ risk may justify continued study therapy.

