## 5.1 Part 1. Dose Escalation

Part 1a of this Phase 1 study will begin with a standard, open-label, 3+3 dose-escalating design of single agent INCB001158 in patients with advanced/metastatic solid tumors. Dose escalation will continue until identification of a maximum tolerated dose (MTD) or to a planned maximum daily dose of 2000 mg orally [i.e., 1000 mg twice daily (BID)]. Dose escalation may continue beyond 2000 mg daily based on emerging clinical data. Escalation will be limited by a maximum pharmacokinetic (PK) threshold based on the exposure at the highest well tolerated doses in GLP-compliant toxicity studies (see Section 10.2.2 for further details).

After achieving a predefined threshold PK target exposure of INCB001158 and/or clear evidence of pharmacodynamic activity (i.e., elevated plasma arginine) during single agent escalation of INCB001158, the safety and tolerability of INCB001158 will be evaluated in combination with the anti-PD-1 agent pembrolizumab in a separate dose escalation (Part 1b). Pembrolizumab will be administered at the dose of 200 mg intravenously (IV) every 3 weeks. Only dose levels of INCB001158 that have already been demonstrated to be safe as a monotherapy will be tested in combination with pembrolizumab.

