#### Pembrolizumab

Pembrolizumab will be administered on day 1 of each 3-week treatment cycle after all procedures and assessments have been completed as detailed on the schedule of assessment. Pembrolizumab will be administered as a dose of 200 mg using a 30-minute IV infusion. Sites should make every effort to target infusion timing to be as close to 30 minutes as possible. However, given the variability of infusion pumps from site to site, a window between -5 minutes and +10 minutes is permitted (i.e., infusion time is 30 minutes -5 min/+10 min). Patients will continue to receive pembrolizumab until disease progression (per irRECIST), intolerable toxicity, patient withdraws consent, or the Investigator determines that is not in the patient's best interest to remain on study. The maximum duration of pembrolizumab treatment on study will be up to 35 doses (approximately 2 years).

Pembrolizumab (Keytruda®) is supplied either as a 50 mg, lyophilized powder in single-use vials for reconstitution or as a 25 mg/mL sterile solution for infusion in 4 mL vials. The dose recently approved in the United States and several other countries for treatment of melanoma patients is 2 mg/kg Q3W. Please refer to the pembrolizumab Label/Investigator's Brochure for specific instructions on pembrolizumab administration.

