### 13.4 INCB001158 Accountability, Reconciliation, and Return

On Day 1 of Cycle 1, patients will be provided with enough INCB001158 to last until their next clinic visit. For patients in Parts 1a and 2, patients will return on Day 1 of each cycle thereafter and will receive a 28-day supply of INCB001158; the number of capsules or tablets remaining from the previous visit will be counted and recorded.

For patients in Parts 1b and 3, patients will return on Day 1 of each cycle thereafter and will receive a 21-day supply of INCB001158; the number of capsules or tablets remaining from the previous visit will be counted and recorded.

The Investigator or designee must maintain an accurate record of dispensing the study drug in a Drug Accountability Log, a copy of which must be given to the Sponsor at the end of the study. The Drug Accountability Log will record the study drugs received, dosages prepared, time prepared, doses dispensed, and doses destroyed. The Drug Accountability Log will be reviewed by the field monitor during site visits and at the completion of the study.

If evidence of tampering is observed, notify the Sponsor and return the questionable INCB001158 shipment with the appropriate form to the contract distribution center. Returned and unused INCB001158 study drug may also be destroyed and documented at the investigative site in accordance with approved site/institution standard operating procedures.

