**ATTACHMENT 1B: SCHEDULE OF STUDY ASSESSMENTS FOR PARTS 1B, 1C, AND 3 (INCB001158 + PEMBROLIZUMAB)**

Cycle Length = 21 Days

Visit	Screening	Cycle 1			Cycle 2	Cycle 3	Cycle 4+	End of Treatment	Follow-Up	
		Day 1	Day 8 (± 2 days) 	Day 15 (± 2 days) 					Day 1 (± 5 days) 	Day 1 (± 5 days) 
Written Informed Consent	X									
Inclusion/Exclusion Criteria	X									
Demographics and Medical History	X									
Physical Examination 	X	X	X	X	X	X	X 	X	X	X
Height	X									
Weight	X	X	X	X	X	X	X 	X	X	X
Vital Signs 	X	X	X	X	X	X	X	X	X	X
ECOG Performance Status	X	X			X	X	X 	X	X	X
Duplicate 12-lead ECG with QTcF 	X	X 		X 				X		
Urinalysis	X	X 			X	X	X	X		
Serum Chemistry levels 	X	X 	X	X	X	X	X	X		
Hematology 	X	X 	X	X	X	X	X	X		
Pregnancy Test 	X				X			X		

Visit	Screening	Cycles						End of Treatment	Follow-Up		
		Cycle 1	Cycle 2	Cycle 3	Cycle 4+	Safety	Disease Status				
	Day-21 to -1	C1D1	C1D8 (± 2 days) 	Day 15 (± 2 days) 	Day 1 (± 5 days) 	Day 1 (± 5 days) 	Day 1 (± 5 days) 	Within 28 days post treatment discontinuation	30-37 days after last dose of INCB001158 + pembrolizumab	90-97 days after last dose of INCB001158 + pembrolizumab	Q9W after discontinuation
Plasma Ammonia Levels 		X	X	X	X	X	X				
Urine Sample for Orotic Acid 		X	X	X	X	X	X				
Coagulation tests	X	X 	X	X	X	X	X	X			
Pharmacokinetic (PK) Assay 		X		X	X	X	X				
Amino Acid Panel 		X		X	X	X	X				
Pembrolizumab Dosing 		X			X	X	X				
INCB001158 Dosing 		X	X	X	X	X	X				
Radiographic Evaluation of Tumor Burden (diagnostic CT or MRI) 	X 						X 	X			X
Adverse Events		X	X	X	X	X	X	X	X	X	
Concomitant Medications	X	X	X	X	X	X	X	X	X	X	
Post-treatment anticancer therapy status									X	X	X

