  13. Patients enrolled in Parts 1b, 1c, and 3: Pembrolizumab dosing will take place on D1 of every cycle. Study treatment with pembrolizumab should be administered on Day 1 of each cycle after all procedures/assessments have been completed. All study treatments will be administered on an outpatient basis. Infusion of pembrolizumab precede INCB001158 dosing and PK analysis on C1D1 and day one of every cycle.
  14. INCB001158 is given daily, BID. During PK days, the morning dose of INCB001158 will be administered during the clinic visit after all pre-dosing procedures, including pembrolizumab administration and pre-dose PK blood sampling, has occurred. INCB001158 will be taken within 5 minutes after pembrolizumab infusion.
  15. Whenever possible, imaging should be done at the same institution/facility and with the same modality that will be used to measure response during the patient's participation in the study. The redacted copies of the reports will be submitted and the scans must be sent to a reader for exploratory analyses. If available, 1-3 redacted scan reports for scans that occurred prior to screening will be requested.
  16. Tumor assessments within 28 days prior to C1D1 will be accepted.
  17. Completed approximately every 9 weeks per RECIST v1.1 OR Modified RECIST for pleural mesothelioma. Evaluations may occur more frequently as clinically indicated.
- [REDACTED]
20. Orotic acid and plasma ammonia samples will also be collected on day one of every cycle after Cycle 4.

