4.1.5. Cycle Length and Duration

Cycle 1 Day 1 is the day that the first dose of INCB001158 or pembrolizumab is administered. The scheduled cycle length is 28 days for participants in Parts 1a and 2. The scheduled cycle length is 21 days for participants in Parts 1b, 1c, and 3.

INCB001158 dosing will not be adjusted for body weight or surface area. Participants will continue to receive INCB001158 until disease progression (confirmed per iRECIST), intolerable toxicity, consent withdrawal, or the investigator determines that it is not in the participant's best interest to remain on-study.

- **INCB001158:** In Part 1, INCB001158 will be administrated PO BID with the dose corresponding to cohort assignment. In Parts 2 and 3, INCB001158 will be administrated PO BID at the RP2D determined in Part 1 as long as the participant is deriving benefit and has not met any of the protocol-defined conditions for treatment withdrawal.
- **Pembrolizumab:** 200 mg IV on Day 1 of each 21-day cycle. The maximum duration of pembrolizumab treatment on-study will be up to 35 doses (approximately 2 years).

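### After a 1-7 day infusion delay, Protocol 12.2 sets later visits every 2 weeks, which contradicts the 21-day pembrolizumab cycle used everywhere else

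*Protocol*

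**What the plan says.** Protocol 12.2 covers infusions that cannot be given at their scheduled visit. Of such an infusion it says "it has to be administered as soon as possible". For a delay of 1 to 7 days, the procedures of the original visit are performed, and then "subsequent visits will follow every 2 weeks (the infusion at the original schedule visit will be considered a missed dose".

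INCB001158 is oral, so the paragraph can only concern pembrolizumab. The rest of the plan gives one interval for it:

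- Protocol 5.1: "Pembrolizumab will be administered at the dose of 200 mg intravenously (IV) every 3 weeks".
- Protocol 13.1, and the Synopsis in the same sense: "Pembrolizumab will be administered on day 1 of each 3-week treatment cycle".
- Attachment 1B, for Parts 1b, 1c and 3: "Cycle Length = 21 Days", with footnote 13 adding "Pembrolizumab dosing will take place on D1 of every cycle".
- Protocol 13.4, for Parts 1b and 3: "patients will return on Day 1 of each cycle thereafter and will receive a 21-day supply of INCB001158".
- SAP 4.1.5, and SAP Table 2 likewise: "200 mg IV on Day 1 of each 21-day cycle".

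After Cycle 1, the combination schedule has only Day 1 visits while treatment continues, each with a window of ±5 days (Synopsis, Study Schedule/Procedures; Attachment 1B).

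**The concern.** Section 12.2 is the instruction a site consults when an infusion slips, and it applies to every combination patient. It cannot be followed together with Attachment 1B. A visit 14 days after the last one is either a Day 1 visit held too soon or a visit that the schedule of assessments does not list.

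What is at stake is the timing of visits and of the assessments tied to Day 1. Sites would also differ in practice, with some following 12.2 and others the 21-day schedule.

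**Working it through.** **Which interval is the outlier.** One stated figure tests the interval. Protocol 13.1 caps pembrolizumab at 35 doses and describes this as about 2 years.

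- At 21 days: 35 × 21 = 735 days; 735 / 365.25 = 2.01 years. This reproduces the stated figure.
- At 14 days: 35 × 14 = 490 days; 490 / 365.25 = 1.34 years. This does not.

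The monotherapy parts use 28-day cycles, so a 2-week interval fits no part of the study.

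**How far visits move.** Inputs:

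- Cycle length 21 days (Attachment 1B), so the second infusion is due on Day 22.
- Delay d = 1 to 7 days (12.2).
- Visit interval after the delay 14 days (12.2).
- Window ±5 days (Attachment 1B).

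Section 12.2 does not say whether the 2 weeks run from the late infusion or from the original date. Nor does it say whether the 21-day schedule is kept or restarted from the late infusion. All four combinations are shown for the k-th later visit.

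| Visits counted from | Compared with | Days early | k = 1 | k = 2 |
|---|---|---|---|---|
| Late infusion: 22 + d + 14k | Original schedule: 22 + 21k | 7k − d | 0 to 6 | 7 to 13 |
| Late infusion: 22 + d + 14k | Restarted schedule: 22 + d + 21k | 7k | 7 | 14 |
| Original date: 22 + 14k | Original schedule: 22 + 21k | 7k | 7 | 14 |
| Original date: 22 + 14k | Restarted schedule: 22 + d + 21k | 7k + d | 8 to 14 | 15 to 21 |

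The most lenient case is d = 7 in the first row. The first later visit is on Day 22 + 7 + 14 = 43, exactly as scheduled (22 + 21 = 43). The second is on Day 22 + 7 + 28 = 57, against Day 22 + 42 = 64, so it is 7 days early. The largest shift is d = 7 in the last row: Day 22 + 28 = 50 against Day 22 + 7 + 42 = 71, or 21 days early.

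Every value at k = 2 exceeds the 5-day window. The due day cancels in each difference, so the result is the same whichever infusion is delayed.

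**The case against.** The best defence is that this is one stray sentence. The 3-week interval is stated without ambiguity in many places, a competent site would follow those, and no effect on dose or data has been shown. That is fair as to weight. It does not make the sentence right, because 12.2 is the provision written for exactly this situation.

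Three further points limit the finding:

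- A delay of 1 to 5 days may already fall within the ±5-day window and never be handled as a delay. A delay of 6 or 7 days clearly triggers the rule.
- The first later visit can be on time, and the 21-day maximum pairs visits counted from the original date with a restarted schedule, which is the least natural reading. The conclusion needs only the 7-day minimum.
- The Synopsis allows additional visits in some cycles for safety, efficacy or pharmacokinetic monitoring. Section 12.2, however, describes how visits continue after a delay, not extra ones.

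A reader might infer more than the documents support:

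- **2-weekly dosing.** If infusions moved with the visits, a patient would receive 200 × 42/14 = 600 mg per 6 weeks instead of 200 × 42/21 = 400 mg, or 1.5 times the plan. But 12.2 refers to visits, and the dosing sections fix infusions to Day 1 of a 3-week cycle. This is a possible misapplication, not what the text prescribes.
- **Lost DLT evaluability in Part 1b.** Protocol 5.1.2 requires two pembrolizumab doses to be received within 42 days. A second infusion moved from Day 22 to Days 23-29 is still received within that window, whatever the original date is called. Protocol 10.2.2.1 also describes the dose-escalation parts as completed.
- **Miscounted exposure.** SAP 6.4 counts cycles and infusions with a nonzero dose and sums the amounts given. Calling the original date missed changes none of these. SAP 6.5 calculates compliance for INCB001158 only.

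For the same reasons, the missed-dose wording is not a second error. The late infusion is plainly to be given, and it is the infusion at the original visit that is called missed.

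**Conclusion.** The contradiction is real: 12.2 gives a 14-day visit interval where every other schedule gives 21 days. It is an internal inconsistency in an operative site instruction, not a design choice. Followed literally, it puts the second visit after the delay at least 7 days early under every reading, outside the ±5-day window.

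This assumes a delay of 1 to 7 days handled under 12.2 as written. The number of such delays is not given, so the total effect cannot be sized. No sample size, type I error, power or endpoint figure is affected.

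**What to change.** In the sentence of Protocol 12.2 on delays of 1 to 7 days, replace the 2-week interval with every 3 weeks. As an optional clarification, state there that the late infusion is that cycle's dose.

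The cost is a wording change to one sentence, or a short addition to it. The design, the SAP and the planned analyses stay as they are.
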